#### Antenatal breastmilk expression

- a)** Number of weekly expressions in the intervention group, measured through weekly push messages. Reported as median and IQR, and illustrated by a barplot figure over the number of weekly expression pr. women.
- b)** Amount of breastmilk expressed if any. How many women will be capable of expressing any milk before birth in the intervention group (counts and percentages), and how many mL (median and IQR). Volume is measured by each woman using a container with an mL scale and reported through weekly self-reported push messages. Milk volumes will be illustrated by a scatterplot over milliliter pr. week compared to the week of gestation.

#### **4.5 Missing data**

Missing data will not be imputed. We will only use the data available.

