In a pilot randomized study, we will include 60 healthy pregnant women. We will allocate 30 women to start aBME from week 34+0 of pregnancy until delivery and compare them to 30 women who does not perform aBME. All women included in this study will receive standard care, and have an individual consultation with a breastfeeding trained midwife in week 33 of their pregnancy. The women allocated to the intervention group will besides breastfeeding consultancy, also be taught how to perform aBME and store breastmilk correctly during the midwife consultation. To detect any signs of uterine contractions or fetal influence a cardiotocography (CTG) will be performed in the intervention group before, during and after the first aBME. In total 40 minutes of CTG surveillance. If the CTG is unclear, it will be assessed by the obstetric doctor in charge of this study, [name] or a substitute. In case of pathological CTG, the women will be send to the obstetric emergency department for further assessment. If the CTG is normal the women in the intervention group can perform aBME 5 minutes from each breast two times per day from week 34 until birth, and collect and store any expressed milk. They will be provided with a schedule to register their aBME sessions (Please see attachment).

Participants will receive both written and oral information about the trial and the intervention group will in addition receive safe storage of MOM (please see attachment 1, 2) and be provided with the needed syringes and labels for expressed milk. Participants will be instructed to be aware of precautions

related to aBME such as: continuous excessive painful contractions, vaginal bleeding or decreased fetal movements. In case of such symptoms they have to contact obstetric emergency department. During the intervention and 8 weeks after birth the participating women will receive weekly push-messages through an application on their smartphone. The messages include short questions about the aBME as well as regarding feeding of the infant after birth. At the end of the study we want to evaluate the mothers experience with the study through an online questionnaire. The questionnaire will be submitted as a supplement to this protocol when finished. All data is managed through OPEN/REDCap and stored in a secure server ([OPEN - Open Patient data Explorative Network - forside \(rsyd.dk\)](http://OPEN - Open Patient data Explorative Network - forside (rsyd.dk)))

Trial design

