In general the evidence in aBME is limited. A few prospective studies has been conducted, and only one larger RCT. This RCT included 635 participants, where aBME was performed from week 36 of pregnancy. They were not able to detect any difference in gestational age at birth or report any adverse events in relation to the aBME. Before the larger RCT they conducted a pilot study, which consisted of 43 participants. Our aim with this study is to primarily test safety and feasibility with the procedure aBME from week 34, and since no study has been done from this week of pregnancy, a reliable power calculation is not possible to make. Therefore we estimated that 30 participants in each group is a realistic and feasible number to include in the pilot study. To detect a difference in gestational age at birth based on 80% power, we estimated that we would need a total of 176 participants, 88 in each group (mean, SD, derived from Soltani et al(19)). If the pilot study shows no trend towards a higher proportion of preterm birth in the intervention group, we will proceed to the larger trial.

Data collection:

Demographic data on the mothers (maternal age, education level, ethnic background, parity and smoking status) will be obtained through medical files. Infant data on gestational age, complications such as preterm contractions or birth and feedings from birth, will be obtained from medical records after birth. To obtain data on aBME and breastfeeding rates after birth, we will use SMS tracking via an app based in the RedCap system. From intervention start until 8 weeks after birth participants in the intervention group will receive a weekly sms, with questions on how many times they stimulated and if they were capable of expressing any milk. The control group will receive a weekly message which regards if they have been giving birth, to be able to initiate the questions on breastfeeding. After birth questions will regard breastfeeding initiation. After eight weeks the mothers experience and evaluation on the study will be evaluated in an online questionnaire.

Data analysis and statistics:

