### 2.2 Adherence to the intervention

We consider all participants who answer weekly questionnaires until 8 weeks post-partum as full completers. E.g. if participants try to follow the intervention as well as possible, but do not stimulate the breast the recommended fourteen times a week, we will still consider them as completers of the study, if they have stayed in the study during the intervention and until eight weeks after birth. However, we will differentiate between study completion and intervention completion. Intervention completion is defined as participants who follow the intervention as well as possible until birth but do not answer all eight questionnaires. These participants will be included in the analysis for gestational age at birth, but will only be included in the breastfeeding analysis as long as they have answered the weekly questions. If participants do not want to perform stimulation anymore, we consider this as a withdrawal of consent. If participants are not adherent to the randomized group, e.g. they start to stimulate antenatal even though they are in the control group, we consider them as excluded from the study.

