### 2.3 Intention to treat (ITT) and per protocol (PP) analysis

We will apply a modified ITT principle, considering only the participants who started the antenatal stimulation and/or participated in the breastfeeding consultation and as the ITT population. Participants who drop out before the breastfeeding consultation for any reason will not be included in any of our analyses. We consider PP as all of the participants who completed questionnaires until 8 weeks post-partum, no matter how well they complied with the intervention. We will apply ITT and PP analysis to our primary and secondary outcomes.

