#### Clinical features on infants

- Gestational age at birth (weeks+days)
- Gender (boy/girl)
- Birthweight (g)
- Birth length (cm)
- Head circumference (cm)
- APGAR score at 1 min (0-10)

- APGAR score at 5 min (0-10)
- Enteral Nutrition PP if hospitalized
- Way of feeding PP if hospitalized
- IV-solutions PP if hospitalized

Breastfeeding rates up to 8 weeks PP (both groups, weekly questionnaires):

- Feeding the first 24 hours (Did your child get anything other than your milk, yes/no)
- Are you breastfeeding (yes/no)
- If yes (Partially or exclusively breastfeeding)

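### Breastfeeding is analysed from answered weekly messages only, with no check on non-response, and the SAP leaves open whether women who stop or start stimulating still supply feeding data

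*SAP*

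**What the plan says.** SAP 4.5 is the whole missing-data plan: "Missing data will not be imputed. We will only use the data available". SAP 2.2 applies the same rule to women who carry on until birth but do not answer every questionnaire: they "will only be included in the breastfeeding analysis as long as they have answered the weekly questions". The source is the weekly message in both groups. The protocol (Data collection) says of stimulation and breastfeeding rates that "we will use SMS tracking via an app based in the RedCap system", and SAP 4.1 lists the feeding items under the weekly questionnaires. Medical records are named for infant feeding from birth and in hospital, but not for the rates over the following weeks.

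SAP 4.2.2 analyses exclusive versus partial breastfeeding (d) and any breastfeeding versus formula (e), from 24 hours to 8 weeks, by mixed effects logistic regression with a bar plot.

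Three further rules decide who supplies data:
- Group A, SAP 2.2: "If participants do not want to perform stimulation anymore, we consider this as a withdrawal of consent".
- Group B, SAP 2.2: if "they start to stimulate antenatal even though they are in the control group, we consider them as excluded from the study".
- Both groups, SAP 2.3: the modified ITT set is defined by "considering only the participants who started the antenatal stimulation and/or participated in the breastfeeding consultation". The per-protocol set is the women who completed questionnaires to 8 weeks.

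SAP 3.4 records reasons for withdrawal but gives them no use in the analysis.

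**The concern.** A likelihood-based mixed model copes with unanswered weeks when the chance of silence depends only on what has already been observed. It does not cope when silence depends on the unreported current state, for example when a woman stops breastfeeding and ignores the next message because of it. Her earlier answers then say breastfeeding, and the event never enters the data.

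The plan has nothing that would show whether this matters. The per-protocol analysis is no check, because it selects further on having answered.

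The rules in SAP 2.2 add a second route. They act before birth, so a woman lost through them has no feeding answers at all and the model has no earlier feeding data from her to use. If such women differ in how they feed their infants, the arms are no longer comparable as randomised. Breastfeeding rates are named in the protocol's objective, and the protocol expects them to improve. A false gap in favour of group A could therefore be read as support.

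**Working it through.** The documents give no expected breastfeeding rate, non-response rate or sample size for these outcomes, so there is no figure of the plan's own to reproduce. The only input from the documents is 30 women per arm (Protocol, Sample Size). All rates below are assumptions. The calculations are for a single visit and are not a refit of the mixed model.

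**Step 1. Silence linked to stopping, equal in both arms.** Let p be the true rate, mb the non-response among breastfeeding women and mn the non-response among those who have stopped.

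Observed rate = p(1 − mb) / [p(1 − mb) + (1 − p)(1 − mn)].

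With p = 0.70 and mb = 0.05:
- mn = 0.10: 0.665 / (0.665 + 0.27) = 71.1%, bias +1.1 points.
- mn = 0.30: 0.665 / (0.665 + 0.21) = 76.0%, bias +6.0 points.
- mn = 0.50: 0.665 / (0.665 + 0.15) = 81.6%, bias +11.6 points.

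The observed odds are the true odds times (1 − mb)/(1 − mn). If that factor is the same in both arms it cancels from the odds ratio. For true rates of 80% and 65% the odds ratio is (0.80/0.20) / (0.65/0.35) = 2.15, and it stays 2.15 in all three cases. The difference in rates shrinks from 15.0 points to 14.6, 12.9 or 10.5. Equal silence therefore distorts the reported rates but not this odds ratio.

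**Step 2. Women lost from group A only.** Let w of 30 be lost, with rate r among them, and a true rate of 70% in both arms.

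Observed rate in A = (0.70 − (w/30)r) / (1 − w/30).

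With r = 0.30:
- w = 1: 0.69/0.9667 = 71.4%, gap +1.4 points, odds ratio 1.07.
- w = 3: 0.67/0.90 = 74.4%, gap +4.4 points, odds ratio 1.25.
- w = 6: 0.64/0.80 = 80.0%, gap +10.0 points, odds ratio 1.71.

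Over r from 0.50 to 0 and w from 1 to 6, the gap runs from +0.7 to +17.5 points (odds ratio 1.03 to 3.0). The true gap is zero throughout.

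**Step 3. Losses in both arms.** If 3 controls who start stimulating are also lost, and 90% of them breastfeed, the observed rate in B is (0.70 − 0.10 × 0.90)/0.90 = 67.8%. Against 74.4% in A (w = 3) the gap is +6.7 points. Under these assumptions the two rules push in the same direction.

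**Step 4. How much missing answers leave open.** With m of 30 missing in each arm, the difference between arms can move by m/30 in either direction from each arm's missing women, so the best-to-worst range is 2m/30 wide. For m = 1, 3 or 6 that is 6.7, 20 or 40 points.

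**Step 5. The two SAP sections side by side.** A group A woman who attended the consultation, started and then stopped stimulating is a withdrawal under SAP 2.2 but belongs to the modified ITT set under SAP 2.3. A control who attended the consultation and later stimulated is excluded under 2.2 but meets the 2.3 definition. SAP 2.3 applies ITT to the secondary outcomes, yet a woman who is no longer messaged has no feeding data and SAP 4.5 supplies none. The text does not say whether she is still messaged.

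**The case against.** The strongest reply is that the mechanism is assumed. No passage says that women who stop breastfeeding tend to stop answering, and the title of one cited Danish cohort report speaks of high participation in weekly text messages on infant feeding. Non-response may be low. That stands: the size of the problem is unknown. It does not remove the need to show response by arm, since a title about another cohort says nothing about this trial's arms.

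Several stronger readings are tempting and should not be made:
- A reader might infer that adherence-based removal affects group A alone. It does not: SAP 2.2 also excludes controls who stimulate, and SAP 3.4 has a category for refusing the instructions of either group.
- A reader might infer that women who stop stimulating are certainly lost. SAP 2.3 leaves that open.
- A reader might infer that the bar plots show raw respondent proportions. SAP 4.2.2 does not say whether they are raw or model-based.
- A reader might build a large gap by assuming that every silent woman has stopped and that silence is 20% in A and 10% in B: 18/24 = 75% against 18/27 = 67%. All of that gap comes from the assumed split. With equal silence it is 18/24 in both arms, and the gap is zero.

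Two technical points also stand. Outcome d is worded as exclusive versus partial. Read literally, it leaves out women who have stopped altogether, so the illustrations fit outcome e more directly. And counting missing as stopped is not neutral. If 6 women in A and 3 in B are missing and share a true rate of 60%, it gives 0.60 × 24/30 = 48% against 0.60 × 27/30 = 54%, a false 6-point gap against A.

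**Conclusion.** The concern holds in limited form. The plan uses answered messages only and tests this nowhere. The mixed model is a reasonable main analysis and is valid if silence depends on observed answers alone. Whether that is so cannot be judged from the documents.

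Silence linked to stopping breastfeeding would inflate the rates (by +1.1 to +11.6 points under the assumptions of step 1). If equal in both arms, it would leave the single-visit odds ratio alone. Bias between arms needs a difference between arms, and the unreconciled rules in SAP 2.2 and 2.3 are the route the documents themselves provide. With 1, 3 or 6 of 30 group A women lost at an assumed 30% rate, against 70% overall, the false gap is +1.4, +4.4 or +10.0 points.

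The documents do not show that such a bias will occur, and nothing here touches the primary outcome. The protocol ties the step to a larger trial to preterm birth, not to breastfeeding. As these are secondary outcomes of a pilot, the severity is minor.

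**What to change.** Keep the mixed model as the main analysis and make four changes.

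1. Reconcile SAP 2.2 with 2.3 so that women who stop stimulating, or controls who start, stay in the breastfeeding follow-up and are analysed as randomised, where consent allows. This concerns data collection and analysis only, not whether anyone should stimulate.
2. The protocol says of the end-of-study questionnaire: "The questionnaire will be submitted as a supplement to this protocol when finished". If it is still open, add one item on the week in which exclusive and any breastfeeding stopped, and use it to fill unanswered weeks. Recruitment had begun when the SAP was written, so this may no longer be possible for everyone, and silent women may skip this questionnaire too.
3. Add sensitivity analyses: missing counted as stopped in both arms, plus best-case and worst-case bounds. The bounds are needed because the first analysis can itself bias the comparison when non-response differs by arm. State the denominator used for outcome d.
4. Report the number responding by arm and week with each bar plot.

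The cost is one questionnaire item, a clarification of two SAP sections and a little more analysis work. The downside is that a recalled week is less exact than a weekly answer. Changes 3 and 4 need no new data.

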#### **4.6 Statistical software**

Statistical analysis will be carried out with Stata® statistical software
